6.1 SCHEDULE OF EVENTS (SOE)

Figure 2: SCHEDULE OF EVENTS

Arm A: Cabozantinib

Assessment	Screening	Day						Relapse-free Follow up
		1 (+/- 3 days)	15 (+/- 3 days)	29 (+/- 3 days)	43 (+ 3 days)	50 (+/- 3 days) ¹	57-85 Safety Follow Up Visit	
	D -42 to -1							3 year follow up (from prostatectomy) ²
Informed consent	X							
Medical history and demographics	X							
Interval history ³		X	X	X		X	X	
Concomitant medicines	X	X	X	X		X	X	
Physical exam and vital signs ⁴	X	X ⁵	X	X		X	X	
Karnofsky Performance Status (KPS)	X	X ⁵	X	X		X	X	
ECG	X							
Randomization ⁶	X							
Toxicity assessment		X	X	X		X	X	
Dispensing of cabozantinib ⁷		X						
Prostatectomy ⁸					X			
Phone call or chart review ⁹								X
Laboratory assessments								
CBC with differential ¹⁰	X ¹¹	X	X	X		X	X	
Serum chemistries (CMP) ¹⁰	X ¹¹	X	X	X		X	X	
Coagulation factors ¹⁰	X ¹¹	X						
PSA ¹⁰	X	X		X			X	
Testosterone ¹⁰	X			X			X	
Thyroid function testing ¹⁰		X		X			X ¹²	
Urine Protein Creatinine Ratio ¹⁰	X ¹¹	X	X	X		X	X	
Correlative/Research studies								
Plasma/serum cfDNA, immune, androgen, and angiome correlates ¹³	X			X			X	
Retrieval of archival prostate biopsy tissue ¹⁴							X	

1. In conjunction with the usual post-operative visit to remove the patient's foley catheter.
2. Follow up will occur every 3 months (+/- 1 month). Follow up may be obtained by a phone call, clinic visit or chart review.
3. Interval history consists of the following:
 - a. Medical history collected as clinically indicated during standard of care clinic visits, which may include disease related symptoms (i.e. pain, changes in urination) and drug related side effects (i.e. bleeding, diarrhea, fatigue, etc.).
 - b. Select imaging to rule out metastatic disease will be done as clinically indicated. Subjects will not routinely receive bone scan, CT, or MRI imaging unless there is clinical concern for possible metastatic disease.
 - c. Interval history during the safety follow-up visit to include review of hospital course while patient underwent prostatectomy.
4. Vital signs must be performed at screening, day 1, day 15, day 29, day 50, and day 57-85 visit by a medical professional. Blood pressure, temperature, pulse, respiratory rate, height (at screening only) and weight will be collected.
5. Day 1 physical exam and KPS do not have to be repeated if screening physical exam and KPS were performed within 7 days prior to Day 1 visit. Vitals signs must be completed on Day 1 regardless of when they were collected during screening.
6. Randomization may take place any time before or on day 1, after the patient is confirmed to be eligible.
7. Cabozantinib will be administered at 40 mg daily for 28 days. A pill diary will be provided to the subject. Study drug will be dispensed directly from the clinic. Unused drug will be returned to the clinic.
8. Prostatectomy will occur 2 weeks (14 + 3 days) after the last dose of cabozantinib. Tissue will be procured for pathologic, molecular, and immunologic assessments.
9. Relapse free survival follow up may be captured over the telephone, clinic visit or chart review every 3 months +/- 1 month.
10. Laboratory assessments at the times indicated include:
 - Complete blood count (CBC) with differential
 - Serum chemistries (CMP): Sodium, Potassium, Chloride, Bicarbonate, blood urea nitrogen (BUN), Creatinine, Glucose, aspartate aminotransferase (AST), alanine aminotransferase (ALT), total bilirubin, alkaline phosphatase, and LDH.
 - Coagulation Factors: PT/INR or PTT will be drawn at baseline only.
 - PSA
 - Testosterone
 - Thyroid function testing: Will include TSH and T4.
 - Urine Protein Creatinine Ratio: $UPCR = (\text{Urine protein mg/dl}) / (\text{urine creatinine mg/dl}) = \text{numerically equivalent to gm protein excreted in urine over 24 hours.}$
 - Notes:** Screening labs (except testosterone) must be completed within 7 days of day 1, or they must be repeated on day 1.
11. CBC with differential, CMP, coagulation factors and urine protein creatinine ratio must be completed within 14 days of Day 1 if subject is assigned or randomized to Arm A: Cabozantinib.
12. Thyroid function tests (TFTs) will be repeated at the safety follow up visit in those who require clinical intervention due to alteration in TFTs at an earlier time point.
13. Immune and androgen correlates will only be collected at baseline and on Day 29.
14. For extraordinary responders (i.e. pCRs) we will obtain archival tissue from their pre-prostatectomy prostate biopsy if available.

FIGURE 3: SCHEDULE OF EVENTS

Arm B: Immediate Prostatectomy

Assessment	Screening	Day	Relapse free Follow up
	D-42 to -1	1 ¹	3 year follow up (from prostatectomy)
Informed Consent	X		
Medical History and Demographics	X		
Interval history ²		X	
Concomitant Medicines	X		
Physical Exam ³	X		
Karnofsky Performance Status (KPS)	X		
ECG	X		
Randomization ⁴	X		
Prostatectomy ⁵		X	
Phone call or chart review ⁶			X
Laboratory assessments			
CBC with differential ^{7,8}	X		
Serum chemistries (CMP) ^{7,8}	X		
Coagulation factors ^{7,8}	X		
PSA ⁷	X		
Testosterone ⁷	X		
Urine Protein Creatinine Ratio ^{7,8}	X		
Correlative/Research studies			
Plasma/serum cfDNA, immune, androgen and angiome correlates	X		

- 1 For this arm, "Day 1" is defined as the day on which the prostatectomy is performed. While the end of screening is labelled as Day -1 and the prostatectomy as Day 1, these days are not intended to be consecutive. It is expected that there will be intervening days in order to allow scheduling of the prostatectomy.
- 2 Interval history consists of the following:
 - a. Medical history collected as clinically indicated during standard of care clinic visits, which may include disease related symptoms (i.e. pain, changes in urination) and drug related side effects (i.e. bleeding, diarrhea, fatigue, etc.).
 - b. Select imaging to rule out metastatic disease will be done as clinically indicated. Subjects will not routinely receive bone scan, CT, or MRI imaging unless there is clinical concern for possible metastatic disease.

- 3 Vital signs must be performed at screening visit by a medical professional. Blood pressure, temperature, pulse, respiratory rate, height and weight will be collected.
- 4 Randomization may take place any time before or on day 1, after the patient is confirmed to be eligible.
- 5 With tissue procurement for pathologic, molecular, and immunologic assessments.
- 6 Relapse free survival follow up may be captured over the telephone, clinic visit or chart review every 3 months +/- 1 month.
- 7 Laboratory assessments at the times indicated include:
 - Complete blood count (CBC) with differential
 - Serum chemistries (CMP): Sodium, Potassium, Chloride, Bicarbonate, blood urea nitrogen (BUN), Creatinine, Glucose, aspartate aminotransferase (AST), alanine aminotransferase (ALT), total bilirubin, alkaline phosphatase, and LDH.
 - Coagulation Factors: PT/INR or PTT.
 - PSA
 - Testosterone
 - Urine Protein Creatinine Ratio: $UPCR = (\text{Urine protein mg/dl}) / (\text{urine creatinine mg/dl}) = \text{numerically equivalent to gm protein excreted in urine over 24 hours.}$
- 8 CBC with differential, CMP, coagulation factors and urine protein creatinine ratio must be completed within 14 days of the completion of screening if the subject randomized to Arm B: Immediate Prostatectomy.

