4.2 CORRELATIVE STUDIES

Please see the lab manual for further details of these analyses.

Apoptosis

Cleaved Caspase-3. Caspase-3 is a central downstream executor of both the intrinsic and extrinsic apoptosis pathways, and is responsible for the proteolytic cleavage of key effector molecules such as nuclear poly (ADP-ribose) polymerase (PARP).²⁹ Cleavage of the zymogen form of caspase-3 to its active p17 and p12 fragments by caspase 8,9,10, or 12 is essential for downstream induction of apoptosis. The primary endpoint is comparison of apoptosis in prostatectomy specimens in cabozantinib-treated patients versus controls.

Comprehensive Immune Profiling

We will focus on comprehensive immune profiling of available samples representing the cabozantinib-treated and untreated tumor microenvironment (TE) as well as baseline and longitudinal PBMC samples in cabozantinib-treated and untreated patients in an attempt to identify both: (1) baseline signatures that predict which patients might benefit from cabozantinib, as well as (2) pharmacodynamic signatures that could provide mechanistic insights regarding therapeutic responses. The TE (tissue) will be analyzed in the laboratory of [name] (Duke Chair of Pathology). The profiling platform to be used to analyze the peripheral blood (PBMC) samples will be highly standardized, polychromatic flow cytometry assays that have been developed by the Duke Immune Profiling Core (DIPC; Director: [name]) specifically for monitoring immune signatures in the context of immune checkpoint blockade trials.

Pathologic Response

Complete pathologic response (pCR) is defined as complete resolution of all cancerous glands in the prostatectomy specimen. Patients treated with cabozantinib who have pCR will be defined as *extraordinary responders*. Tissue from these patients' prostate biopsy will be collected for analysis and correlation with key correlative endpoints.

Relapse-free Survival

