After completion of the treatment period (if applicable), prostatectomy, and safety follow up period (if applicable), patients will be followed for relapse-free survival, so that this rate may be estimated at 3 years (landmarked from the prostatectomy). *Relapse* is defined as biochemical recurrence (AUA guidelines), radiographic evidence of metastasis (in the opinion of the investigator), new treatment for prostate cancer or death. According to AUA guidelines, a biochemical recurrence is defined as a serum PSA ≥ 0.2 ng/mL, which is confirmed by a second determination with a PSA ≥ 0.2 ng/mL.

Apoptosis

TUNEL. Apoptotic index will be assessed in tissue biopsies and prostatectomy specimens from all patients using the TdT nick-end labeling technique.

Proliferation

Ki-67. Proliferation index (PI) will be assessed in tissue biopsies and prostatectomy specimens from all patients.

Angiogenesis

CD31. We will perform immunohistochemistry staining for CD31, an angiogenesis marker, in tissue biopsies and prostatectomy specimens from all patients on formalin-fixed tissue sections that are consecutive to those stained for apoptosis and proliferation.

HGF-c-MET Axis

c-MET. Tumor specimens will be evaluated for c-MET, HGF, and phospho-c-MET expression as a measure of pharmacodynamic response to cabozantinib treatment.

HGF/phospho-c-MET double stain. HGF is the ligand of the c-MET receptor and controls its activity through paracrine activation. HGF is secreted by prostate stromal cells and by inflammatory cells in the prostate stroma. HGF is also secreted by vascular smooth muscle cells. Stroma will be evaluated for expression of HGF as a measure of pharmacodynamic response to cabozantinib treatment.

Plasma Angiome

Blood for use in the plasma angiome multiplex ELISA will be collected as described previously.³⁰ Samples will be stored for possible future processing in the Phase I Biomarker Laboratory at Duke (Director: [name]), Molecular Reference Laboratory for the Alliance Oncology Cooperative Group, a national clinical trial research group sponsored by the National Cancer Institute.

Gene Expression Analysis

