6.13 SAFETY FOLLOW UP VISIT - ARM A ONLY

At the post-surgery follow-up visit, the following procedures should be performed:

- Interval history (to include review of hospital course while patient underwent prostatectomy)
- Assessment of any adverse events and tumor-related signs and symptoms
- Physical examination including major body systems
- Karnofsky Performance Status (KPS), body weight, and vital signs and other tests as necessary to follow unresolved or evaluate new adverse events
- Sample collection for the following laboratory evaluations:
 - Complete blood count (CBC) with differential: WBC count with differential, platelet count, hemoglobin, and hematocrit.
 - Serum chemistries: Sodium, potassium, chloride, blood urea nitrogen (BUN) or urea, creatinine, glucose, carbon dioxide (CO₂) or bicarbonate, aspartate aminotransferase (AST), alanine aminotransferase (ALT), albumin, total bilirubin, alkaline phosphatase, LDH.
 - Urine protein creatinine ratio
 - PSA level
 - Testosterone level
 - Thyroid function testing: TSH and T4. Thyroid function tests (TFTs) will be performed only for subjects who require clinical intervention due to alteration in TFTs at an earlier time point.
- Assessment of concomitant medications, toxicities and treatments
- Plasma/serum biomarker studies
- For extraordinary responders we will obtain archival tissue from their prostate biopsy pre prostatectomy

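### Does the plan need to schedule biopsy retrieval for every patient because Section 4.2 describes TUNEL, Ki-67 and CD31 readings on biopsies from all of them?

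*Combined protocol and SAP*

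**What the plan says.** Section 4.2 (Correlative Studies) names the tissue for each marker:

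- TUNEL: "Apoptotic index will be assessed in tissue biopsies and prostatectomy specimens from all patients using the TdT nick-end labeling technique".
- Ki-67: "Proliferation index (PI) will be assessed in tissue biopsies and prostatectomy specimens from all patients".
- CD31: "an angiogenesis marker, in tissue biopsies and prostatectomy specimens from all patients on formalin-fixed tissue sections".

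The operational sections are narrower. The Arm A schedule in Section 6.1 has one row, "Retrieval of archival prostate biopsy tissue", marked at the Day 57-85 visit. Its footnote 14 reads: "For extraordinary responders (i.e. pCRs) we will obtain archival tissue from their pre-prostatectomy prostate biopsy if available". Section 6.13 repeats this: "For extraordinary responders we will obtain archival tissue from their prostate biopsy pre prostatectomy". The Pathologic Response paragraph of Section 4.2 defines the group, starting "Patients treated with cabozantinib who have pCR will be defined as", so no Arm B patient can belong to it. It adds that tissue from these patients' "prostate biopsy will be collected for analysis and correlation with key correlative endpoints".

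The Arm B schedule has one correlative row, for blood. Section 6.14 lists only surgery and tissue taken at surgery. Section 6.3 (Screening) has no biopsy retrieval for either arm. Section 6 states that tissue is collected at prostatectomy in both arms and refers to the two schedules for the details. Section 4.2 opens by sending the reader to the lab manual.

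**The concern.** A site that works only from the schedules would request archived biopsies for a handful of men at most, and for none in Arm B. Section 4.2, read alone, promises biopsy readings on everyone. If a baseline reading were needed to interpret the marker results, nearly all of it would be missing, and the control arm would have none. A later reader might also be unable to tell whether absent biopsy data were planned or a protocol deviation. A second site is still to be selected, so new staff will depend on the schedules.

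**Working it through.** **1. The plan's own figure.** Section 11.1 gives 10 control and 20 cabozantinib patients, a two-sample t-test and two-sided alpha 0.05. Power comes from the noncentral t distribution with 28 degrees of freedom and noncentrality d × √(10 × 20 / 30).

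| Difference (d, in SD) | Noncentrality | Power | Stated |
|---|---|---|---|
| 1.0 | 2.58 | 70.3% | 70% |
| 1.5 | 3.87 | 96.2% | 96% |

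Both figures reproduce. They concern cleaved caspase-3 in prostatectomy specimens, so no biopsy reading enters them.

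**2. Biopsy readings with no source in the schedules.** Inputs: 30 evaluable men (20 in Arm A, 10 in Arm B) and 3 markers. The documents give no rate of complete response; Section 2.3 expects such responses only in a minority. The rates below are assumptions, and every responder's block is taken to be available.

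- Implied readings: 30 × 3 = 90.
- Biopsies retrieved = 20 × rate. Biopsies without a source = 30 − 20 × rate.

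| Assumed rate in Arm A | Retrieved | Without a source | Readings without a source |
|---|---|---|---|
| 0% | 0 | 30 | 90 of 90 |
| 5% | 1 | 29 | 87 of 90 |
| 10% | 2 | 28 | 84 of 90 |
| 20% | 4 | 26 | 78 of 90 |

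All 10 Arm B biopsies are without a source at any rate. Counting every enrolled man (up to 33 under Section 11.1) would imply 33 × 3 = 99 readings.

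These counts cover biopsy readings only. With the 90 prostatectomy readings added, 78/180 to 90/180 (43% to 50%) of all readings of these markers lack a scheduled source. The half taken at surgery is scheduled in both arms.

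**3. Which planned analysis needs the biopsies.**

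| Where | What it requires |
|---|---|
| Section 3, exploratory objective 3 | Between-arm comparison of the three markers in prostatectomy specimens |
| Section 11.1, Data Analysis | Box plots, summaries and a between-arm t-test |
| Section 11.1, primary endpoint | Cleaved caspase-3 in prostatectomy specimens |

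None of these uses a biopsy value. The plan contains no change from biopsy to surgery and no baseline-adjusted comparison of these markers.

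**4. What footnote 14 is for.** Section 4.2 defines a complete response as no cancerous glands left in the prostatectomy specimen. For these men the diagnostic biopsy is the tumour tissue that remains to study. The retrieval row therefore has a purpose of its own, and it could not supply a before-and-after tumour pair in any case.

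**The case for a change.** The strongest case for a change is that the texts cannot both be followed as they stand. Three marker paragraphs say all patients. The schedules, which Section 6 presents as the full account, provide for complete responders in one arm. Aligning them would cost little: either drop the mention of biopsies from the three paragraphs, or request about 30 archived blocks and make 90 stains. No new biopsy is needed, because inclusion criterion 6 already requires cancer in at least two cores. If the lab manual does ask for every biopsy, the schedules are then out of step with it.

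The inconsistency of wording stands. It is weaker than a flat contradiction, since neither footnote 14 nor Section 6.13 says that no other biopsies may be retrieved, and the lab manual could supply the rest.

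The practical consequence does not stand. Deleting the words changes no analysis. Retrieving every block adds work, some blocks will be missing or exhausted, and no stated analysis improves. Biopsy values could serve as a covariate, but the plan has no such analysis. Whether it would gain precision depends on the biopsy-to-surgery correlation and the number of usable blocks, neither of which the documents give.

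**Conclusion.** This is a minor inconsistency of wording, and no change to the plan follows. It reaches only the biopsy readings of three exploratory markers: 78 to 90 of 90 without a source in the schedules, at an assumed complete response rate of 0 to 20% in Arm A. The primary test, its power, objective 3 and the planned t-tests rest on prostatectomy tissue collected in both arms and are unaffected. Analysts can carry out Section 11.1 as written and report any biopsy readings that exist descriptively. The readings are unscheduled rather than lost, provided that the archived diagnostic blocks are kept. The conclusion assumes that no analysis outside the package depends on these readings; the lab manual could not be checked.

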6.2 INFORMED CONSENT

Authorized study personnel should fully explain the scope of the study to each subject before obtaining informed consent. Subjects should be advised of any known risks inherent in the planned procedures, of any alternative treatment options, of their right to withdraw from the study at any time for any reason, and of their right to privacy.

When obtaining informed consent, study personnel should:

First: Confirm that the subject is a potential candidate for study participation.

Next: Obtain dated and signed informed consent.

Finally: Confirm that the subject is eligible as defined in Section 5.0 (Inclusion/Exclusion Criteria). A record of subjects who fail to meet entry criteria (i.e., screening failures) will be maintained.

For subjects consented at the lead site ONLY, registration in the Duke clinical trial subject registry (i.e. Oncore) must be completed within 1 business day of the subject providing informed consent.

6.3 SCREENING- BOTH ARMS

The screening examination will take place within 42 days of initiation of therapy or surgery. An informed consent form must be signed by the subject before any study-specific screening procedure takes place.

Subject data to be collected at the Screening Examination includes:

- Informed consent process utilizing a signed and dated IRB-approved ICF
- Confirmation of inclusion/exclusion criteria

- Medical history including concomitant illnesses and oncologic history. Oncologic history must include specific documentation of prostate cancer histologic diagnosis.
- Prior and concomitant medications and non-pharmacologic treatments taken within 4 weeks of screening will be recorded.
- ECG
- Sample collection for the following laboratory evaluations (all standard-of-care except PT/INR and PTT):
 - Complete blood count (CBC) with differential: WBC count with differential, platelet count, hemoglobin, and hematocrit.
 - Serum chemistries: Sodium, potassium, chloride, blood urea nitrogen (BUN) or urea, creatinine, glucose, carbon dioxide (CO₂) or bicarbonate, aspartate aminotransferase (AST), alanine aminotransferase (ALT), albumin, total bilirubin, alkaline phosphatase, LDH.
 - Urine protein creatinine ratio
 - Testosterone and PSA levels.
 - Prothrombin time (PT)/INR or partial thromboplastin time (PTT) test.
- Correlative samples will be drawn at screening. See lab manual for details.
- Physical examination to be conducted and height (cm), weight (kg), and vital signs (including temperature [°C], blood pressure [mmHg], heart rate [beats per minute], respiratory rate [breaths per minute]). Height will be collected at screening only.
- Karnofsky Performance Status (KPS)

Once the subject completes the screening examinations and is determined to be eligible, he will be assigned or randomized to arm A or arm B and enrolled.

Arm A

- Cabozantinib will be administered orally at 40 mg daily for 28 days
- 14 day + 3 days washout prior to prostatectomy
- Prostatectomy

Arm B

- Immediate prostatectomy

6.4 SUBJECT REGISTRATION AND ENROLLMENT

After signing informed consent, subjects will be registered with the lead site (Duke) and with their study site/institution. A record of subjects who fail to meet entry criteria (i.e., screen failures) will be maintained.

6.5 LEAD SITE REGISTRATION AND ENROLLMENT

Subject registration for all subjects signing informed consent will be completed by Duke University Medical Center Genitourinary Oncology Group. Following consent, documents will be submitted for review and registration of subject. Consented subjects will be assigned a unique study ID at registration.

Subjects will be enrolled only after all pre-treatment screening evaluations are completed, all eligibility criteria are met and the lead site reviews the Eligibility Checklist. Once the subject has signed consent and been found to meet all eligibility criteria with the approval from the lead site, the subject will be randomized, except for the Safety Lead-In Cohort subjects which will be assigned. Treatment must not commence until the subject has received approval from the lead site.

6.6 INSTITUTIONAL REGISTRATION

Subject registration at each study site/institution will be conducted according to the institution's established policies. Prior to registration, subjects will be asked to sign and date an Institutional Review Board (IRB)-approved consent form. Subjects must be registered with their local site/institution and with the lead site before beginning any treatment or study activities.

